16.0 Statistical Analysis

Power analysis

The effect sizes observed in the completed Prasad et al. 2012 study were used to estimate the sample size necessary for adequate power to detect differences in cognitive variables for the current study. The earlier study, which enrolled 12 patients in each group, saw changes in cognitive function with effect sizes that ranged from small ($d=0.25$) to quite large ($d=1.21$). An intent-to-treat (ITT) analysis will be adopted, which includes all randomized subjects. We will use two cognitive domains from the MATRICS battery, visual memory and working memory, as the primary outcome variables. Prasad reported effect sizes of Cohen's $d=0.79$ for working memory and $d=0.97$ for visual object learning when comparing valacyclovir to placebo in HSV-1-seropositive subjects. Forty percent of patients with schizophrenia are HSV-1 positive (Prasad et al in press; Dickerson et al 2003). A total of 175 subjects will be enrolled at 5 sites, with the expectation that 70 subjects will be HSV-1-seropositive and 105 subjects will be seronegative. With 70 HSV-1 positive subjects enrolled (35 per treatment group), we would be able to detect a minimum effect size of $d=0.63$ (a conservative estimate based on the Prasad study) for each of the two primary outcome measures at significance level $\alpha=0.05$ using two-sided t tests. The Hochberg modification of the Bonferroni method to control Type 1 error will be used. With this method, the smallest of the p-values for the two outcomes is tested at $p<\alpha/2$; if that test is rejected, the second outcome is tested at $p<\alpha$. We will achieve the same power when testing HSV-1 positive vs. negative subjects who are on valacyclovir using similar methods. We will test the treatment effects on the two primary efficacy measures (visual and working memory) with one-tailed tests at an overall $\alpha=0.1$. Stratified randomization will be used to ensure the balance of HSV-1 status between the valacyclovir group and the placebo group.

Data Analysis

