The primary objective of this study is to determine: 1) whether valacyclovir improves cognitive functioning in schizophrenia subjects who are HSV1 seropositive and early in the course of their illness, and 2) whether the improvement from valacyclovir differs in HSV1 seropositive and negative subjects. We hypothesize that subjects who received valacyclovir will show improvement in memory functioning, as measured by the visual and working memory domains of the MATRICS cognitive battery relative to their counterparts who received placebo, and the improvement exists in HSV-1 seropositive subjects compared to the seronegative subjects. All randomized subjects will be used using ITT analysis. This is the most conservative approach for detecting a treatment effect, because the inclusion of subjects who did not complete the intervention will serve to underestimate rather than overestimate any treatment effect. Sensitivity analyses including a subset analysis using completers only analysis will also be performed to test the robustness of the findings. Statistical tests will be performed based on one-sided test at the 10% level of significance with an adjustment for multiple comparisons for the 2 primary efficacy outcome measures with each primary measure tested at an alpha threshold of $p<0.05$ as noted above. One-tailed tests are planned because the main interest of this study is to

determine if valacyclovir is superior to placebo and thus has produced a sufficient efficacy signal in one or more of the two primary efficacy outcome measures to warrant further assessment in subsequent larger, confirmatory trials.

Baseline analysis will be conducted to summarize patients' characteristics in the two treatment groups for HSV-1 seropositive and seronegative subjects respectively. Demographics and relevant clinical variables, including symptom severity and antipsychotic dose equivalents, will be compared between treatment groups using two-sample t tests (for continuous variables) and chi-square tests (for categorical variables).

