The primary outcome measures are the visual and working memory domains of the MATRICS battery. For each subject, a change score will be calculated for this domain, which quantifies the difference in cognitive performance from pre-treatment baseline to post randomization study visits. Unadjusted p-values from direct comparison of valacyclovir vs. placebo among HSV-1 positives, and HSV-1 positive vs. negative with active treatment will be reported using two-sample one-sided t tests.

The primary outcome measures (visual memory and working memory) and important secondary cognitive (MCCB composite score) and functional (UPSA-B, Q-LES-Q-SF) outcome measures will be assessed at baseline, visit 6 and visit 10. To analyze these measures, we will employ a mixed model for repeated measures ANCOVA, of the general form for each measure: Post-baseline score at visit i = baseline score + treatment + visit + HSV-1 status + interactions among treatment, visit, and HSV-1 status + other baseline covariates, where visit is a categorical measure denoting whether the post baseline score came from visit 6 or 10. Within-subject correlation will be modeled with an unstructured covariance matrix with 3 parameters (variances at visit 6 and 10, covariance between visits 6 and 10). In this model, the treatment effect estimates the average magnitude of the treatment differences at visits 6 and 10, and the treatment x visit interaction the difference in the magnitude of the treatment difference at visit 10 vs visit 6. Additional interactions involving treatment, HSV-1 and week estimate how the magnitude of treatment differences, on average or at visits 6 versus 10, is altered by HSV-1 status. No imputation will be needed to address missing data issue using the linear mixed model approach.

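### Two analyses and several visit summaries are planned for the same primary outcomes, and none is named as the test that decides the primary aim

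*Combined protocol and SAP*

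**What the plan says.** All of this is in section 16.0 of the combined protocol and SAP.

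- **Method A.** Under Data Analysis, change from baseline is to be compared by two-sample one-sided t tests: "Unadjusted p-values from direct comparison of valacyclovir vs. placebo among HSV-1 positives", and likewise seropositive against seronegative subjects on active drug. Post-randomization visits are mentioned in the plural, and none is chosen.
- **Method B.** The next paragraph, covering the same outcomes, reads "To analyze these measures, we will employ a mixed model for repeated measures ANCOVA". The model uses visits 6 and 10, adjusts for baseline, and includes HSV-1 status and its interactions. Its treatment term is described as the between-arm difference averaged over the two visits, and a treatment by visit term captures how that difference changes.
- **Error control.** "We will test the treatment effects on the two primary efficacy measures (visual and working memory) with one-tailed tests at an overall" alpha of 0.1, "with each primary measure tested at an alpha threshold of" p<0.05. Also: "The Hochberg modification of the Bonferroni method to control Type 1 error will be used". Both statements concern the two outcomes only.
- **Population and missing data.** "All randomized subjects will be used using ITT analysis". A completers-only analysis is listed as a sensitivity analysis. The statement that imputation is unnecessary refers to the mixed model; no rule is given for the t tests.
- **Power.** The detectable effect of d=0.63 with 35 per group is based on comparisons "using two-sided t tests".

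**The concern.** The plan's signals point in different directions. The power statement, and the only comparison written out as valacyclovir against placebo in HSV-1 positives, belong to the t test. The full model specification and the only missing-data statement for these outcomes belong to the MMRM. The MMRM itself offers the two-visit average and, through the visit interaction, visit-specific differences. With HSV-1 interactions in the model, the seropositive effect required by the Primary Aim (section 3.0) has to be built as a contrast, and the plan does not define it.

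The result is several eligible p-values per outcome and an alpha split that allows for none of that choice. At stake is whether a reported signal carries the one-sided 10% error rate that the plan states, which is already lenient.

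**Working it through.** **The plan's own figures.** The split is 0.10/2 = 0.05 per outcome. With two independent outcomes and one test each, the chance of at least one false positive is 1 − 0.95² = 0.0975, so the stated 10% holds for a single prespecified analysis. The d=0.63 has no stated power. The normal formula gives (1.960 + 0.674) × √(2/35) = 0.63, that is, 75% power for a two-sided 0.05 t test. The sample-size statement was therefore framed around the t test.

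**Inputs for the error rate.**
- From the documents: 35 per arm, two outcomes, follow-up at visits 6 and 10, overall one-sided alpha 0.10, and test-retest reliability of about 0.7 (section 8.0, MCCB), used as the correlation between times.
- Assumed: time correlation varied over 0.5–0.8; correlation between outcomes 0–0.5; dropout either none, or 10% by visit 6 and 20% by visit 10, unrelated to outcome.

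**Method.** Data were simulated under no treatment effect, 20,000 trials in each of five scenarios. Baseline-adjusted ANCOVA in HSV-1 positives stands in for the MMRM. A false positive is any rejection in any analysis left open. Simulation standard error near 0.10 is √(0.10 × 0.90/20,000) = 0.002. The smallest-p column rejects if either outcome has p<0.05. The Hochberg column also rejects if both have p<0.10.

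| Analyses from which success may be claimed | Smallest p<0.05: correlations 0.7 (time), 0.3 (outcomes) | Smallest p<0.05: range | Hochberg: range |
|---|---|---|---|
| One prespecified test | 0.093–0.097 | 0.085–0.097 | 0.091–0.101 |
| Visit-10 t test or visit-10 ANCOVA | 0.122 | 0.111–0.130 | 0.117–0.135 |
| Visit-10 t test or ANCOVA average | 0.142 | 0.130–0.144 | 0.137–0.150 |
| t test at visit 6 or visit 10 | 0.164 | 0.152–0.165 | 0.160–0.170 |
| Either method at either visit | 0.210 | 0.189–0.220 | 0.199–0.228 |
| Both methods at visit 6, visit 10 or average | 0.220 | 0.198–0.233 | 0.207–0.241 |

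A repeat with outcome correlations of 0.3–0.4 and each test at one-sided 0.05 agreed: about 9% for one test, 13–15% for the visit-10 t test or the model average, 17–19% when the visit-6 t test is added, and up to 23% with visit-specific adjusted tests as well.

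**Precision.** With unit variances and correlation r, the change score has variance 2(1 − r) and the baseline-adjusted score 1 − r². At r=0.7 these are 0.60 and 0.51; 0.60/0.51 = 1.18. The ratio equals 2/(1 + r), so it is 1.33 at r=0.5 and 1.11 at r=0.8.

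**Average against visit 10 within the adjusted analysis.** At r=0.7 throughout, the adjusted variance of the average is (1 + 0.7)/2 − 0.49 = 0.36, against 0.51 at visit 10; 0.51/0.36 = 1.42.

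**Missing data.** A change score needs an observed follow-up value. Section 10.0 leaves assessments at discontinuation to the investigator's discretion, so missing scores are foreseeable. Unless values are imputed, the t test uses only subjects with an observed follow-up score.

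**The case against.** The best defence is that the MMRM is plainly the main analysis. It is fully specified, it names visits 6 and 10 and their average, and the t-test p-values are merely to be reported. Basing power on a t test is common and does not make it a rival. That is a fair reading, and it is right that only the t test lacks a fixed visit. It does not close the gap: the text never says the model decides, and never names the seropositive contrast. The word unadjusted could mean without covariates or without multiplicity correction, so it does not settle the status of the t tests.

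Three stronger readings are tempting and are not supported.

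- **That the plan inflates the error rate outright.** No sentence permits claiming success from any favourable analysis. The excess arises only if that choice is made, which the plan leaves open.
- **That a complete-case test carries the ITT conclusion.** The t test is nowhere called the ITT analysis, and the completers-only analysis is explicitly a sensitivity analysis. The point rests on silence about missing data.
- **That the t test is biased where the MMRM is not.** The documents give no dropout rate or pattern for this trial, and section 2.0 reports similar dropout in both arms of the pilot. The MMRM depends on missingness being explained by observed data, and a subject lost before visit 6 contributes no outcome to it either.

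The precision argument is also limited, because the adjusted model is already planned; the loss matters only if the t test decides. Finally, the trial seeks a signal to justify larger confirmatory trials, which lowers the stakes.

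**Conclusion.** The concern holds in conditional form. The two primary outcomes have two methods and more than one visit summary, no deciding test, no named HSV-1-positive model contrast, and multiplicity control over outcomes only. As written, the plan does not secure its stated 10% one-sided error rate. With one prespecified test the rate is about 9–10%. With free choice it is about 13–15% for the visit-10 t test or the model average, and up to about 23% (24% under the Hochberg rule) with every option open. These figures rest on assumed correlations and on ANCOVA in HSV-1 positives standing in for the full 175-subject model. No bias from dropout is established. This should be corrected before analysis, but it does not invalidate the design.

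**What to change.** 1. Make the MMRM contrast of valacyclovir against placebo in HSV-1 positives the single deciding test for each primary outcome.
2. Fix one summary for it: the plan's own average over visits 6 and 10, or visit 10 if the sponsor prefers. Visit 10 changes the estimand and, if the effect is constant over visits, raises the variance by about 42% at r=0.7.
3. Apply the two-outcome multiplicity procedure to that contrast.
4. Name the treatment by HSV-1 status contrast from the same model as the test for the second primary objective, which otherwise has no deciding test.
5. Label the unadjusted t tests and the remaining visit summaries as supportive, say what unadjusted means, and state how missing scores are handled in the t tests.

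The cost is a few sentences in section 16.0, plus a deliberate choice of estimand if visit 10 is taken. The real concession is that a favourable supportive result can no longer be claimed as primary.

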1.0 Introduction

Schizophrenia is a serious mental illness whose etiology is unknown. Cognitive impairments are a prominent feature of the illness and contribute to the social disability that is common in individuals with the disorder.¹ Currently there are no established treatments for the cognitive impairments associated with the disorder. A previous pilot study found that early course individuals with schizophrenia who were seropositive for the Herpes Simplex Virus 1 (HSV-1) and received adjunctive valacyclovir showed improvement in performance on some cognitive tasks compared to those who received adjunctive placebo.² Schizophrenia subjects who were HSV-1 seronegative were excluded from the trial. The current study is undertaken to confirm and extend these findings and determine if HSV-1 seropositive status confers cognitive enhancing effects of valacyclovir.

We intend to test the hypothesis that cognitive functioning in early course schizophrenia will be improved by treatment with the antiviral drug, valacyclovir, in subjects who are seropositive for HSV-1. We will enroll 70 adult subjects who are HSV-1 positive and 105 who are HSV-1 negative across US study sites; subjects will be individuals early in the course of schizophrenia. Subjects will be randomized to receive adjunctive valacyclovir, 1.5 g twice per day, or placebo over the 16 weeks of the trial. All subjects will continue to seek regular medical care and adhere to a regimen of psychiatric medications prescribed by their treating psychiatrist.

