In a recent pilot study at the University of Pittsburgh, Prasad et al randomized 24 HSV-1 seropositive individuals with schizophrenia who were within 10 years of illness onset to receive valacyclovir 1 g orally twice daily for 2 weeks followed by 1.5 g orally twice daily for 16 weeks vs. identical appearing placebo.² All patients were maintained on prescribed antipsychotic medication throughout the course of the trial. At the end of the trial, subjects in the valacyclovir group showed significantly greater improvement in - working memory and visual memory than did subjects receiving adjunctive placebo. There were no significant differences between groups in psychotic symptom severity or in other cognitive domains. The medication was well tolerated by study subjects and the dropout rates were similar between the valacyclovir and the placebo group. Because there was not a HSV-1 seronegative comparison group, it could not be determined if the seropositivity of the cohort was the key factor that contributed to the positive cognitive results.

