3.0 Specific Aims

The Primary Aim of the Study is:

1. To determine the efficacy of adjunctive valacyclovir, in comparison to placebo, to improve visual (Brief Visuospatial Memory Test) and working (composite score of the Spatial Span and Letter Number Span tests) memory in individuals who are HSV-1 positive and early in the course of schizophrenia. We hypothesize that individuals who are HSV-1 positive, but not those who are HSV-1 negative, will demonstrate significant valacyclovir efficacy for visual and working memory.

The Secondary Aims of the Study are:

1. To evaluate the efficacy of adjunctive valacyclovir, in comparison to placebo, to improve general cognitive performance as measured by the MATRICS composite score in HSV-1 positive and negative subjects.
2. To evaluate the efficacy of adjunctive valacyclovir, in comparison to placebo, to improve functional performance and quality of life as measured by the USCD Performance-Based Skills Assessment, Version B (UPSA-B), Quality of Life Enjoyment and Satisfaction Questionnaire – Short Form (Q-LES-Q-SF) and Personal and Social Performance Scale (PSP) and to improve global functional assessments as measured Clinical Global

Impressions Severity Scale (CGI-S) and Clinical Global Impressions Severity Improvement scale (CGI-I) scores in HSV-1 positive and negative subjects.

3. To evaluate the efficacy of adjunctive valacyclovir, in comparison to placebo, for general and positive symptoms as measured by the PANSS total and Marder subscale factor scores and negative symptoms as measured by the NSA-16 in HSV-1 positive and negative subjects.
4. To evaluate the tolerability and safety of valacyclovir treatment in this population.
5. To explore changes in the levels of inflammatory markers - HSV2, CMV, EBV, CRP, and Toxoplasmosis – and their relationship to treatment outcomes.

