The MCCB will be administered according to Attachment 1. It is a reliable cognitive battery (test-retest reliability ~0.7 for most tests. Small but statistically significant practice effects have been noted with speed of processing and problem-solving subtests (1/5th of standard deviation). To overcome these practice effects, alternate forms of MCCB will be implemented in this study. The total average administration time of MCCB is approximately 75 minutes. MCCB is comprised of seven cognitive domains and 10 related tests (Trail Making Test: Part A; Brief Assessment in Cognition in Schizophrenia: Symbol Coding; Hopkins Verbal Learning Test-Revised; Wechsler Memory Scale-Third Ed: Spatial Span; Letter-Number Sequencing; Neuropsychological Assessment Battery: Mazes; Brief Visuospatial Memory Test-Revised; Category Fluency: Animal Naming; Mayer-Salovey-Caruso Emotional Intelligence Test: Managing Emotions; and Continuous Performance Test-Identical Pairs. For each cognitive test, a multi-item score will be derived based on the raw item values according to the MCCB scoring manual. Each of the individual item raw scores is standardized to age- and gender-corrected t-scores (mean=50, standard deviation=10). Each test will be converted in to a domain score, with Working Memory and Speed of Processing domains consisting of 2 and 3 tests, respectively. The visual and working components of the MCCB will be administered first because they represent the primary aims of the study.²²

UCSD Performance-Based Skills Assessment-B (UPSA-B)

The UPSA-B is a performance-based assessment of improvement in functional capacity. Participants are asked to role-play tasks in 2 areas of functioning: communication and finances. The communication subtest revolves around a series of 9 role-play exercises using an unplugged telephone. The finance subtest tests the patient's ability to count change, read a utility bill, and write checks. Scores are assigned for each of the 2 subscales and a provided formula is used to calculate an UPSA-B Total Score (range = 0-100).²³

Personal and Social Performance Scale (PSP)

The PSP scale is a 100-point, single item, clinician rated scale to assess 4 domains of functioning, including personal and social relationships, socially useful activities, self-care and disturbing and aggressive behaviors.²⁴

Quality of Life Enjoyment and Satisfaction Questionnaire – Short Form (Q-LES-Q-SF)

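### Whether the valacyclovir benefit differs by HSV-1 status is a primary question, but no test is named to decide it, and the only serostatus comparison given power has no placebo control

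*Combined protocol and SAP*

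**What the plan says.** The protocol's section 1.0 says the trial is to "determine if HSV-1 seropositive status confers cognitive enhancing effects of valacyclovir". Section 2.0 explains why: the pilot enrolled only seropositive patients, so "it could not be determined if the seropositivity of the cohort was the key factor". The Data Analysis part of section 16.0 makes this part 2 of the primary objective: "whether the improvement from valacyclovir differs in HSV1 seropositive and negative subjects". Improvement is described there as relative to patients on placebo.

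Three statements bear on how part 2 would be answered.

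- **Power (section 16.0, Power analysis).** After giving a detectable effect of 0.63 for 35 versus 35 seropositive patients, the plan adds "We will achieve the same power when testing HSV-1 positive vs. negative subjects who are on valacyclovir using similar methods".
- **t tests (section 16.0, Data Analysis).** Unadjusted p-values are promised for valacyclovir versus placebo among positives, and "HSV-1 positive vs. negative with active treatment will be reported using two-sample one-sided t tests".
- **Mixed model (section 16.0, Data Analysis).** Post-baseline scores at visits 6 and 10 are modelled on baseline, treatment, visit, HSV-1 status and their interactions: "Additional interactions involving treatment, HSV-1 and week estimate how the magnitude of treatment differences", on average or at one visit against the other, depend on HSV-1 status.

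Section 3.0 words the hypothesis differently again: "individuals who are HSV-1 positive, but not those who are HSV-1 negative, will demonstrate significant valacyclovir efficacy for visual and working memory".

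**The concern.** Part 2 asks about a difference between two placebo-controlled differences. The t test compares positives with negatives who all took valacyclovir. Patients were not randomised to a serostatus, and the untreated change in each serogroup is not removed. Differences between the serogroups in natural course, practice or regression to the mean therefore count as drug effect. About 52 seronegative placebo patients contribute nothing to this test.

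The protocol itself gives reason to expect such differences. Section 2.0 reports that HSV-1 seropositivity predicts worse cognition, and that HSV-1-related brain impairment seems to progress in early-course patients.

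The mixed model has the right comparison, but the plan only says what its terms estimate. It does not say that the interaction decides part 2, at which visit, or with what power. If the t test and the interaction disagree, the plan does not say which one answers the question. A reader who relies on the t test could report HSV-1-specific efficacy that is not there, or miss specificity that is.

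**Working it through.** **Inputs from section 16.0.** There are 70 seropositive and 105 seronegative patients, randomised 1:1, which gives 35 per arm in positives and about 52.5 per arm in negatives. The effect is 0.63 SD. The analysis sets one-sided 0.05 for each primary outcome; the power paragraph uses two-sided 0.05, so both are shown.

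**Assumptions.** Change-score SD is 1 in all four cells. Unless stated, there is no effect in negatives and no dropout.

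**The plan's own figure.** The plan gives no power level for 0.63 with 35 per arm, so no single figure can be reproduced. By the t distribution, power is 74% at two-sided 0.05 and 83% at one-sided 0.05.

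**Standard errors in SD units**

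- Valacyclovir versus placebo in positives: √(2/35) = 0.239
- Positives versus negatives on valacyclovir: √(1/35 + 1/52.5) = 0.218
- Interaction: √(2/35 + 2/52.5) = 0.309, which is 0.309/0.239 = 1.29 times the first

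**Power at 0.63 SD, single-visit change scores** (noncentral t; 68, 85.5 and 171 df)

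| Contrast | One-sided 0.05 | Two-sided 0.05 |
|---|---|---|
| Treatment effect in positives | 83% | 74% |
| Within valacyclovir | 89% | 81% |
| Interaction | 65% | 53% |

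The same-power sentence is therefore fair, even slightly modest, for the contrast it names. It does not carry over to the interaction. The interaction detectable with 80% power is 0.77 SD one-sided (0.87 two-sided). With 20% dropout (28 per arm and 42 per arm), interaction power is 57% (44%). With an effect of 0.2 SD in negatives, the interaction is 0.63 − 0.20 = 0.43 SD and power is 40% (28%).

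**Bias of the within-valacyclovir test.** Let δ be the untreated difference in change, positives minus negatives. The test's expected value is the true interaction, plus δ, plus nothing that removes δ. The documents give no size for δ, so a range is shown (one-sided 0.05).

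| Size of δ | Inactive drug, δ positive: rejection rate | True effect 0.63 in positives only, δ negative: power |
|---|---|---|
| 0 | 5% | 89% |
| 0.1 | 12% | 78% |
| 0.2 | 23% | 62% |
| 0.3 | 39% | 44% |

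A simulation (40,000 trials per setting, normal data, 35/35 positives and 53/52 negatives) gave rejection rates for the within-valacyclovir test under an inactive drug of 0.1%, 0.5%, 5.0%, 23.7% and 39.1% at δ = −0.3, −0.2, 0, +0.2 and +0.3. The interaction test stayed at 4.9–5.1% throughout and kept 65% power.

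**Baseline-adjusted mixed model.** Section 8.0 gives "test-retest reliability ~0.7 for most tests". Assume one common correlation ρ among baseline, visit 6 and visit 10, and equal effects at both visits. Setting the change-score SD to 1 makes the score variance 1/(2(1−ρ)), which is 1.667 at ρ = 0.7. The residual variance is then:

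- one visit: 1.667 × (1 − 0.49) = 0.85
- two-visit average: 1.667 × (0.85 − 0.49) = 0.60

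Multiplying the standard errors by √0.85 or √0.60 (170 df) gives, at one-sided 0.05:

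| ρ = 0.7 | One visit | Two-visit average |
|---|---|---|
| Interaction | 71% | 84% |
| Interaction, 20% dropout | 63% | 76% |
| Treatment effect in positives | 89% | 96% |

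For ρ from 0.5 to 0.8, interaction power without dropout runs from 76% down to 69% for one visit, and from 89% down to 81% for the average.

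**The case against.** The strongest reply is that the plan already contains the answer. The t tests are introduced as unadjusted direct comparisons, and the mixed model follows as the way to analyse the measures. Its interaction terms describe part 2 closely. The model's treatment effect is defined as the average over visits 6 and 10, so the average can be read as the default. For that average, power is about 84% at ρ = 0.7, and the pilot effects of 0.79 and 0.97 would give 82% and 93% even on single-visit change scores at one-sided 0.05.

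The size of the bias is also assumed. Section 2.0 points towards seropositive patients worsening, which suggests lost power more than false positives. Section 8.0 specifies alternate test forms and reports practice effects for other domains. Finally, the trial is described as looking for a signal.

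Much of this is fair. The right model exists, and power may be adequate under favourable assumptions. But those points depend on a contrast that the plan never designates. It does not call the t test descriptive; it gives that test power alongside the main efficacy comparison. The pilot effects come from 12 patients per group, and the plan itself chose 0.63 as the conservative value. Lost power from worsening in positives is still a wrong answer to part 2. The signal-finding rationale concerns superiority to placebo, whereas seronegative patients, 105 of 175, are there to answer the serostatus question.

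**Conclusion.** The concern holds. A primary question has no declared test, and the one serostatus comparison given power does not answer it. The structural fault needs no assumption: the within-valacyclovir contrast cannot separate drug specificity from an untreated difference between serogroups.

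Its practical size does depend on assumptions. Untreated differences of 0.1 to 0.3 SD move false rejection from 5% to between 12% and 39%, or cut power from 89% to between 78% and 44%, according to direction.

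The power of the proper test cannot be read from the plan. With no dropout, no seronegative effect and one-sided 0.05, it ranges from 65% (single-visit change score) to 84% (two-visit adjusted average at ρ = 0.7). The choice of visit within the mixed model alone accounts for 13 points (71% against 84%). Dropout or some effect in negatives lowers all of these. The matter should be fixed before unblinding, but it does not undermine the design.

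**What to change.** Name one test for each part of the primary objective, both from the mixed model already specified and at one stated visit or the stated average of visits 6 and 10.

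- **Part 1:** valacyclovir minus placebo within HSV-1 positives.
- **Part 2:** that difference in positives minus the same difference in negatives.

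State the alpha and sidedness for part 2 (section 16.0 already sets one-sided 0.05 per outcome) and how it relates to part 1. Align the hypothesis in section 3.0, since a significant result in positives and a non-significant one in negatives is not a test of a difference.

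Label the within-valacyclovir t test descriptive. Replace the same-power sentence with the interaction's own power for the chosen contrast, giving the assumed correlations, dropout and seronegative effect. If the 65% / 0.77 SD (one-sided) or 53% / 0.87 SD (two-sided) figures are quoted, mark them as single-visit change-score figures without dropout.

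The cost is protocol and SAP wording and two contrast statements, with no new patients, visits or data. The drawback is that the stated power for part 2 will look less favourable than for part 1.
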